6.3.4 ADDITIONAL INFORMATION REGARDING MYELODYSPLASTIC SYNDROME AND ACUTE MYELOID LEUKEMIA

Based on an analysis of myelodysplastic syndrome (MDS) and acute myeloid leukemia (AML) conducted in May 2014, 9 cases were identified (4 MDS and 5 AML), 4 of which (2 MDS and 2 AML) were reported by the investigator as related to carfilzomib. Of the 9 cases, 7 are from company-sponsored clinical studies, 2 are from ISTs and none were identified from the postmarketing experience.

A medical review of the 9 cases revealed that 8 of the events of MDS/AML were reported in the setting of underlying relapsed/refractory multiple myeloma in subjects previously treated with multiple chemotherapy regimens and radiation; 2 of these 8 subjects also had a prior history of MDS prior to study entry. The ninth case was reported from an IST for subjects with underlying relapsed AML and acute lymphoblastic leukemia, and thus, this report of AML did not represent a new disorder for that subject.

There is an inherent increased risk of developing secondary malignancies in multiple myeloma patients, including MDS and AML independent of therapy. Approximately 10,000 cases of MDS are diagnosed annually in the US, corresponding to an annual age- adjusted incidence rate of approximately 3.3 to 3.4 per 100,000. Using population-based data from Sweden, there is an 11.51-fold (95% CI: 8.19–15.74) increased risk of AML/MDS for patients diagnosed with MM, including both treated and untreated patients, compared with Swedish general population, corresponding to an incidence rate of 139 per 100,000 person-years (Mailankody 2011). Prior treatment exposure to other chemotherapy agents including

melphalan, lenalidomide, and thalidomide contribute to the risk; MDS and/or AML are documented in the labeling for these agents.

All 9 subjects had other risk factors (e.g., prior treatment exposure to other chemotherapy agents including melphalan, lenalidomide, and thalidomide; all of which include MDS and/or AML documented in their labeling). Three of the 9 subjects actually had a previous diagnosis of MDS or AML at study entry. Therefore, a meaningful causal association with the administration of carfilzomib could not be established. Events of MDS or AML will continue to be monitored in the clinical study and postmarketing setting.

Finally, in addition to these 9 cases, 5 cases (2 MDS and 3 AML) were reported in the 1110 control arm subjects enrolled into 1 of 4 ongoing, company-sponsored, Phase 3 clinical studies. None of these 5 subjects were exposed to carfilzomib. These 5 cases serve to emphasize the elevated inherent risk for MDS/AML experienced by myeloma patients independent of treatment exposure.

6.3.5 ADDITIONAL INFORMATION REGARDING TOXICITY

6.3.5.1 Increased Creatinine or Decreased CrCl

No dose adjustment is required in patients with mild, moderate, or severe renal impairment or patients on chronic dialysis. Since dialysis clearance of carfilzomib concentrations has not been studied, the drug should be administered after the dialysis procedure. The renal safety profile of carfilzomib provides evidence of its tolerability in heavily pretreated patients with multiple myeloma and concomitant renal insufficiency (Harvey 2012). A PK study (Study PX-171-005) was conducted in 50 multiple myeloma subjects who had various degrees of renal impairment. Carfilzomib was administered IV over 2 to 10 minutes, on 2 consecutive days, weekly for 3 weeks (Days 1, 2, 8, 9, 15, and 16) every 28 days. Subjects received an initial dose of 15 mg/m2, which could be escalated to 20 mg/m2 starting in Cycle 2, if 15 mg/m2 was well tolerated in Cycle 1. Escalation of the carfilzomib dose to 27 mg/m2 at Cycle 3 and beyond was allowed for subjects who tolerated the 20 mg/m2 dose in Cycle 2. Results from this study suggest that subjects with mild to severe renal dysfunction, including dialysis patients, can receive CFZ at doses shown to be efficacious and well-tolerated in multiple myeloma patients with normal renal function.

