The clinical development program for carfilzomib has provided the ability to assess safety across patient populations with a broad spectrum of baseline characteristics relevant to the indicated patients with multiple myeloma, including patients with the following characteristics in Phase 2 and 3 multiple myeloma studies: (1) advanced disease; Onyx Pharmaceuticals, Inc. Investigator's Brochure Carfilzomib for Injection (2) refractory and heavily pretreated; (3) newly diagnosed disease; (4) multiple comorbidities (e.g., renal insufficiency and renal failure, anemia, thrombocytopenia, or cardiovascular disease); (5) pre-existing peripheral neuropathy; (6) prior bortezomib therapy (including a substantial number of patients with multiple myeloma refractory to bortezomib or who cannot tolerate bortezomib); (7) various ages (age range of 21 to 91 years); (8) similar proportion by sex to the general population; and (9) a substantial proportion of patients of African American ethnicity.

The safety profile remains consistent with the mechanism of action of proteasome inhibitors, but with predictably lower rates of peripheral neuropathy, based on the epoxyketone structure that improves proteasome inhibition selectivity. Extensive analysis in renally impaired patients has indicated that no dose adjustment for baseline renal insufficiency is required. The independent efficacy of carfilzomib monotherapy also obviates the need for high doses of steroids, making the carfilzomib regimen steroid-sparing and an important treatment option for patients who need to avoid the toxicity associated with therapeutic doses of corticosteroids. Analysis of the substantial proportion of patients who continued on carfilzomib therapy for extended durations indicated that the drug was well tolerated, without cumulative or late-effect toxicity.

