6.2.3 DOSE ESCALATION SCHEME - FOR PHASE I ONLY

Dose escalation will proceed within each cohort according to the following scheme. Dose-limiting toxicities (DLT) are defined above.

Number of Subjects with DLT at a Given Dose Level	Escalation Decision Rule
0 out of 3	Enter 3 subjects at the next dose level.
> 2	Dose escalation will be stopped. This dose level will be declared the maximally administered dose (highest dose administered). Three (3) additional subjects will be entered at the next lowest dose level if only 3 subjects were treated previously at that dose.
1 out of 3	 Enter at least 3 more subjects at this dose level. a. If 0 of these 3 subjects experience DLT, proceed to the next dose level. b. If 1 or more of this group suffer DLT, then dose escalation is stopped, and this dose is declared the maximally administered dose. Three (3) additional subjects will be entered at the next lowest dose level if only 3 subjects were treated previously at that dose.
≤ 1 out of 6 at highest dose level below the maximally administered dose	This is generally the recommended phase II dose. At least 6 subjects must be entered at the recommended phase II dose.

6.2.4 PHASE II PORTION OF THE STUDY

AGENT	DOSE	ROUTE	DAYS	INTERVAL
Irinotecan	125 mg/m ²	IV infusion (over 90 min)	1, 8, 15	q 28 days
Carfilzomib	20/36 mg/m ²	IV infusion (over 30 min)	1, 2, 8, 9 15 and 16	q 28 days

* Cycle 1 Day 1 & Day 2 doses are 20 mg/m2. All subsequent days as specified, i.e. 20/27 mg/m2 means Cycle 1 Day 1 & Day 2 doses are 20 mg/m2 and all other days are 27mg/m2.

Additional cycles of therapy may be administered provided the subject meets all of the

following at the **beginning of each cycle**:

- ANC \geq 1,500/µL.
- Platelet count $\geq 100,000/\mu L$.
- All other Grade 2, 3 or 4 non-hematological toxicities have resolved as required in section 6.3.3.
- Serum creatinine $\leq 1.5 \text{ x}$ ULN OR measured or calculated creatinine clearance $\geq 60 \text{ mL/min}$ using the Cockcroft-Gault.

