6.3.3 DOSE REDUCTIONS OF CARFILZOMIB AND IRINOTECAN FOR NON-HEMATOLOGIC TOXICITIES

Dose adjustment guidelines for non-hematologic toxicities that occur at any point during the prior cycle are summarized as follows:

Event name	Recommended Action	Recommended Action
Grade of Event	Carfilzomib	Irinotecan
Allergic reaction/hypersensitivity		
Grade 2 – 3	Hold until ≤ Grade 1, reinstitute at full dose.	No change in dose
Grade 4	Discontinue	No change in dose
Tumor lysis syndrome $(\geq 3 \text{ of following:} \geq 50\% \text{ increase in creatinine, uric acid, or phosphate;} \geq 30\% \text{ increase in potassium;} \geq 20\% \text{ decrease in calcium; or } \geq 2-\text{fold increase in LDH}$	Hold carfilzomib until all abnormalities in serum chemistries have resolved. Reinstitute at full doses.	Hold irinotecan until all abnormalities in serum chemistries have resolved. Reinstitute at full doses.
Infection Grade 3 or 4	Hold carfilzomib until systemic treatment for infection complete. If no neutropenia, restart at full dose. If neutropenic, follow neutropenic instructions.	Hold irinotecan until systemic treatment for infection complete. If no neutropenia, restart at full dose. If neutropenic, follow neutropenic instructions.
Peripheral Neuropathy Grade 2 treatment emergent with pain or Grade 3neuropathy	Continue to dose. If neuropathy persists for more than two weeks hold carfilzomib until resolved to ≤ Gr 2 without pain. Then restart at 1 dose decrement if indicated.**	No change in dose
Peripheral Neuropathy Grade 4 neuropathy	Discontinue	Discontinue
Serum creatinine elevation Grade 2, 3 or 4	Hold until ≤ Grade 1. Resume at one dose level lower, if indicated.**	Hold until ≤ Grade 1. Resume at one dose level lower, if indicated.**

Hepatic Impairment Grade 3 or 4 elevation of transaminases or bilirubin	Hold Carfilzomib until < Grade 2. Resume at one dose level lower, if indicated.**	Hold Irinotecan until < Grade 2. Resume at one dose level lower, if indicated.**
Congestive heart failure Grade 3 or 4	Any subject with symptoms of grade 3 or 4 congestive heart failure, whether or not drug related, must have the dose held until resolution to grade 2 or less, or return to baseline, after which treatment may continue at 1 dose decrement, or the subject may be withdrawn from the study. If no resolution after 2 weeks, the subject will be withdrawn from the study.	No change in dose

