Death due to cardiac arrest has occurred within a day of carfilzomib administration. New onset or worsening congestive heart failure or myocardial ischemia have occurred following administration of carfilzomib. Cardiac failure events (e.g., cardiac failure congestive, pulmonary edema, and ejection fraction decreased) were reported in 7% of patients. Monitor for cardiac complications and manage promptly. Unless otherwise specified in the individual protocol, withhold carfilzomib for Grade 3 or 4 cardiac events until recovery and consider whether to restart carfilzomib based on a benefit/risk assessment. Patients with NYHA Class III and IV heart failure, myocardial infarction in the preceding 6 months, or conduction abnormalities uncontrolled by medications were not eligible for the clinical studies. These patients may be at greater risk for cardiac complications. Dyspnea, predominately Grade 1 and 2, was reported in 35% of subjects enrolled in clinical studies (see Section 6.7, Undesirable Effects). Evaluate patients with dyspnea based on the clinical presentation and manage accordingly. Unless otherwise specified in the individual protocol, reduce or interrupt dose as appropriate.

6.3.5.6 Hepatic Toxicity

Cases of hepatic failure, including fatal cases, have been reported (< 1%). Carfilzomib can cause elevations of serum transaminases and bilirubin. Monitor liver enzymes frequently. Please use section 6.3.3 as a guide to reduce or interrupt carfilzomib dose.

6.3.5.7 Posterior Reversible Encephalopathy Syndrome

Posterior reversible encephalopathy syndrome (PRES), formerly termed reversible posterior leukoencephalopathy syndrome (RPLS), is a rare, neurological disorder, which can present with seizure, headache, lethargy, confusion, blindness, altered consciousness, and other visual and neurological disturbances, along with hypertension. The diagnosis is confirmed by neuroradiological imaging. If diagnosed early and treated, the symptoms of PRES may be reversed. Cases of PRES have been reported in patients receiving carfilzomib. Discontinue carfilzomib if PRES is suspected. The safety of reinitiating carfilzomib therapy in patients previously experiencing PRES in not known.

6.3.5.8 Conditions Not Requiring Dose Reduction

The following conditions are exceptions to the above guidelines. Carfilzomib does not need to be held in the following cases:

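### Section 6.3.5.1 says no dose adjustment is needed for any renal impairment, without limiting this to baseline, and so conflicts with the carfilzomib hold and reduction for raised creatinine in 6.3.3

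*Combined protocol and SAP*

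**What the plan says.** Two parts of the dose-modification section speak to renal function.

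- **Section 6.3.3**, non-hematologic toxicities, has a row for "Serum creatinine elevation Grade 2, 3 or 4". The action is the same in the carfilzomib and irinotecan columns: "Hold until ≤ Grade 1. Resume at one dose level lower, if indicated". The table is introduced as dose adjustment guidance for toxicities arising in the prior cycle.
- **Section 6.3.5.1**, Increased Creatinine or Decreased CrCl, sits under the additional toxicity information in 6.3.5. Its first sentence reads: "No dose adjustment is required in patients with mild, moderate, or severe renal impairment or patients on chronic dialysis". It goes on to dialysis timing and to a pharmacokinetic study that "was conducted in 50 multiple myeloma subjects who had various degrees of renal impairment". It does not mention 6.3.3.

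Four other places bear on how the two fit together.

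- Section 1.3.5 gives the limited form of the statement: "no dose adjustment for baseline renal insufficiency is required".
- The hepatic entry, 6.3.5.6, does hand over to the table: "Please use section 6.3.3 as a guide to reduce or interrupt carfilzomib dose".
- The cycle-start criteria in 6.2.4 require creatinine of no more than 1.5 times "ULN OR measured or calculated creatinine clearance" of at least 60 mL/min. They also require that other Grade 2 to 4 non-hematologic "toxicities have resolved as required in section 6.3.3".
- Section 6.3.5.8 lists the exceptions to the hold rules. Creatinine is not among them.

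**The concern.** A site that finds a raised creatinine on treatment has two instructions for carfilzomib. One holds the drug and may lower the dose. The other, under the heading that best matches the finding, says no adjustment is needed at any degree of impairment. Nothing states which prevails.

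This is a safety instruction. Section 9.3.1 lists raised creatinine and renal failure requiring dialysis among the common carfilzomib effects. Section 1.3.3 reports a Grade 3 renal failure, considered possibly related, on Cycle 1 Day 2 at 20 mg/m2. A site that follows 6.3.5.1 literally would keep dosing through a renal toxicity that 6.3.3 treats as a reason to stop.

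**Working it through.** The plan gives no figure for this point, so the check compares the texts and then sizes the doses in dispute.

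**1. Do the two rules cover the same event?** The heading of 6.3.5.1 names a change in creatinine or clearance, and the section sits among on-study toxicities. Its sentence covers all degrees of impairment with no baseline limit. The 6.3.3 row covers a creatinine rise of Grade 2 or more. Read literally, both apply to that rise. Section 6.3.3 calls its own actions dose adjustments, so a hold cannot be set aside as something else.

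**2. Which drug?** Section 6.3.5.1 discusses carfilzomib. Nothing contradicts the irinotecan hold.

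**3. Does the cited study support continuing?** It enrolled myeloma subjects who already had renal impairment and gave 15 mg/m2, rising to at most 27 mg/m2. It does not address a new rise on 36 mg/m2 with irinotecan.

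**4. Which doses?**

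- *Dose level on resuming.* Section 6.3.3 plainly covers this, because it acts on toxicity from the prior cycle. Under 6.3.1 one level below 20/36 is 20/27, and reductions are permanent. Over a full later cycle the difference is 6 × (36 − 27) = 54 mg/m2, against 6 × 36 = 216 mg/m2, or 54/216 = 25%. The reduction applies only if indicated.
- *Remaining doses of the current cycle.* The prior-cycle wording of 6.3.3 does not expressly order an in-cycle hold. Two things suggest it is meant: 6.3.1 foresees carfilzomib being held on Days 2, 8, 9, 15 and 16, and the Phase II calendar tests creatinine before treatment on Days 8 and 15. On that reading the most that is in dispute, per event found at a scheduled test, is:

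| Found | Doses | Amount | Share of Cycle 2+ (6 × 36 = 216) | Share of Cycle 1 (2 × 20 + 4 × 36 = 184) |
|---|---|---|---|---|
| Day 8, unresolved to Day 16 | 4 | 4 × 36 = 144 mg/m2 | 144/216 = 67% | 144/184 = 78% |
| Day 15, unresolved to Day 16 | 2 | 2 × 36 = 72 mg/m2 | 72/216 = 33% | 72/184 = 39% |

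Rises that resolve sooner put fewer doses in dispute.

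**5. How many subjects?** The documents give no rate for this regimen. As an illustration only, section 1.3.4 reports Grade 3/4 renal impairment of 2.2% in myeloma at 20/27 mg/m2 with hydration and low-dose dexamethasone. Applied to 88 registrations:

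- Expected subjects: 88 × 0.022 = 1.94; 95% binomial range 0 to 5.
- Chance of at least one: 1 − 0.978^88 = 0.86.
- At half the rate (1.1%): 0.97 expected, 1 − 0.989^88 = 0.62. At double (4.4%): 3.87 expected, 1 − 0.956^88 = 0.98.

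These figures count renal events. A disputed dose also needs the event to be unresolved when the next dose is due or to call for a reduction, and the site to follow 6.3.5.1 rather than 6.3.3. No input exists for those steps. Nor is there a Grade 2 rate under prophylaxis. Section 1.3.3 reports Grade 2 rises in three of five myeloma subjects at 27 mg/m2 before prophylaxis, and section 1.3.4 describes rises in the later studies as mostly below Grade 2.

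**The case against.** The strongest reply is that the two sections concern different things: 6.3.3 a graded event, 6.3.5.1 a type of patient. The references to dialysis, concomitant renal insufficiency and the renal study all fit pre-existing impairment. Nor is that reading empty here: inclusion criterion 7 accepts normal creatinine or clearance of at least 60, so a subject with normal creatinine and lower clearance can enter. Creatinine is missing from the exceptions in 6.3.5.8, the irinotecan hold stands beside the carfilzomib hold in the same row, the cycle-start criteria impose a renal threshold, and 6.3.5.11 gives a contact for dosing questions.

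Most of this stands. It shows that 6.3.3 was probably meant to govern and that the cycle-start criteria limit the exposure. It does not remove the conflict, because a site must infer the precedence from other sections, and the heading of 6.3.5.1 points the other way.

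It is also fair that many of the reported rises were benign. Those at 27 mg/m2 reversed quickly and did not recur on rechallenge (1.3.3), and section 1.4 attributes the rises seen with bolus dosing to a pre-renal cause. That bears on the likely harm of continuing, but it does not say which instruction to follow.

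A reader might infer two stronger claims. One is that 6.3.3 expressly orders a hold on Days 8 and 15; its prior-cycle wording makes that the likely reading, not the stated one. The other is that there is an 86% chance of a disputed dose; that figure is the chance of any Grade 3/4 renal event at a rate from another disease, dose and infusion time.

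**Conclusion.** The concern holds as an unresolved conflict between two carfilzomib dosing instructions, and it should be corrected. It reaches the dose level on resuming, including in the next cycle. If 6.3.3 is taken to apply within a cycle, it also reaches the remaining doses of the current one, at most four (144 mg/m2) per event found at a scheduled test. The in-cycle figures rest on that reading and on the rise staying unresolved to Day 16.

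The number of subjects affected is unknown. The figure of about 2 of 88 assumes that the myeloma rate carries over, and even the direction of error in that assumption is unclear. The documents do not support extending the point to irinotecan or to the trial's statistical design: sample size, power and the primary analysis are unaffected.

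**What to change.** Replace the first sentence of 6.3.5.1 with:

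> No carfilzomib dose adjustment is required for renal impairment present at baseline. For a Grade 2-4 creatinine rise on study, whether found during a cycle or before the next one, follow the serum creatinine row of 6.3.3.

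Leave 6.3.3 unchanged, including its tumor lysis row. This restores the baseline limit already used in 1.3.5, adds the kind of cross-reference already used in 6.3.5.6, and settles the in-cycle question for creatinine. The cost is two sentences of amendment text, with no added visits, tests or subjects.

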6.3.5.2 Infections

Subjects with grade 3 or 4 active or suspected infections should have treatment withheld until infection has resolved and anti-infective treatment has been completed. After the infection has resolved and anti-infective treatment has been completed, treatment may continue at the original dose. If there is no resolution of toxicity after 3 weeks, the subject will be withdrawn from the study.

6.3.5.3 Congestive Heart Failure (CHF)

Any subject with symptoms of grade 3 or 4 CHF or any other suspected acute cardiac event, whether or not drug related, must have the dose held until resolution. After the event has resolved or returned to baseline, treatment may continue at 1 dose decrement, with the approval of the Medical Monitor, or the subject may be withdrawn from the study. If there is no resolution of CHF after 2 weeks, the subject will be withdrawn from the study.

6.3.5.4 Pulmonary Hypertension

Pulmonary arterial hypertension was reported in 2% of patients treated with carfilzomib and was Grade 3 or greater in less than 1% of patients. Evaluate with cardiac imaging and/or other tests as indicated. Unless otherwise specified in the individual protocol, withhold carfilzomib for pulmonary hypertension until resolved or returned to baseline and consider whether to restart carfilzomib based on a benefit/risk assessment.

6.3.5.5 Myocardial Infarction

Death due to cardiac arrest has occurred within a day of carfilzomib administration. New onset or worsening congestive heart failure or myocardial ischemia have occurred following administration of carfilzomib. Cardiac failure events (e.g., cardiac failure congestive, pulmonary edema, and ejection fraction decreased) were reported in 7% of patients. Monitor for cardiac complications and manage promptly. Unless otherwise specified in the individual protocol, withhold carfilzomib for Grade 3 or 4 cardiac events until recovery and consider whether to restart carfilzomib based on a benefit/risk assessment. Patients with NYHA Class III and IV heart failure, myocardial infarction in the preceding 6 months, or conduction abnormalities uncontrolled by medications were not eligible for the clinical studies. These patients may be at greater risk for cardiac complications. Dyspnea, predominately Grade 1 and 2, was reported in 35% of subjects enrolled in clinical studies (see Section 6.7, Undesirable Effects). Evaluate patients with dyspnea based on the clinical presentation and manage accordingly. Unless otherwise specified in the individual protocol, reduce or interrupt dose as appropriate.

6.3.5.6 Hepatic Toxicity

Cases of hepatic failure, including fatal cases, have been reported (< 1%). Carfilzomib can cause elevations of serum transaminases and bilirubin. Monitor liver enzymes frequently. Please use section 6.3.3 as a guide to reduce or interrupt carfilzomib dose.

6.3.5.7 Posterior Reversible Encephalopathy Syndrome

Posterior reversible encephalopathy syndrome (PRES), formerly termed reversible posterior leukoencephalopathy syndrome (RPLS), is a rare, neurological disorder, which can present with seizure, headache, lethargy, confusion, blindness, altered consciousness, and other visual and neurological disturbances, along with hypertension. The diagnosis is confirmed by neuroradiological imaging. If diagnosed early and treated, the symptoms of PRES may be reversed. Cases of PRES have been reported in patients receiving carfilzomib. Discontinue carfilzomib if PRES is suspected. The safety of reinitiating carfilzomib therapy in patients previously experiencing PRES in not known.

6.3.5.8 Conditions Not Requiring Dose Reduction

The following conditions are exceptions to the above guidelines. Carfilzomib does not need to be held in the following cases:

- Grade 3 nausea, vomiting or diarrhea (unless persisting > 3 days with adequate treatment of antiemetics or anti-diarrheals)
- Grade 3 fatigue (unless persisting for >14 days)

Neither Carfilzomib nor Irinotecan need to be held in the following cases:

- Alopecia
- \geq Grade 3 hyperglycemia attributed to dexamethasone

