3.2 NUMBER OF CENTERS

A minimum of 8 investigative study sites will participate on this trial.

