Pulmonary Hypertension Grade 2, 3, or 4	Hold Carfilzomib until < Grade 2. Resume at one dose level lower, if indicated.**	No change in dose
Diarrhea		
Grade 2 or Grade 3 lasting < 3 days*	No change in dose	Hold Irinotecan until < Grade 2. Resume at same dose level.
Grade 3 (lasting > 3 days) or 4*	Hold Carfilzomib until < Grade 2. Resume at one dose level lower, if indicated.**	Hold Irinotecan until < Grade 2. Resume at one dose level lower, if indicated.**
*Recommended management: Loper onset, followed by 2 mg with each loo 16 mg/24 hours) Adjunct anti-diarrhe	amide antidiarrheal therapy dosage ose motion until diarrhea-free for 1 al therapy is permitted and should	schedule: 4 mg at first 2 hours (maximum dosage: be recorded when used.
Nausea/Vomiting		
Grade 2	No change in dose.	Hold Irinotecan until < Grade 2. Resume at same dose level.
Grade 3	No change in dose	Hold Irinotecan until < Grade 2. Resume at one dose level lower, if indicated.**

Grade 4	Hold Carfilzomib until < Grade 2. Resume at one dose level lower, if indicated. **	Hold Irinotecan until < Grade 2. Resume at one dose level lower, if indicated. **						
Other Non-Hematologic Toxicity								
Other non-hematologic toxicity assessed as drugrelated \geq Grade 3	Hold dose until toxicity resolves to < Grade 2 or baseline. Resume at one dose level lower, if indicated. **.	Hold dose until toxicity resolves to < Grade 2 or baseline. Resume at one dose level lower, if indicated. **.						
*Subjects requiring a delay of >3 weeks should go off protocol therapy. **Subjects requiring > two dose reductions should go off protocol therapy.								

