9.3.2 ADVERSE EVENTS AND POTENTIAL RISKS FOR IRINOTECAN

Irinotecan is FDA approved for all cancers treated in this clinical trial. Please refer to the package insert for a full adverse event listing. Risks and side effects related to Irinotecan include those which are:

Likely Side Effects: those occurring in more than 20% of subjects (or more than 20 out of 100 persons) who received Irinotecan:

- Thrombocytopenia that could result in bleeding including serious and life-threatening bleeding
- Anemia
- Changes in liver function. These changes are usually detected by blood test only and are not associated with any symptoms. These changes usually do not require treatment.
- Fatigue
- Constipation
- Nausea or vomiting
- Leukopenia and neutropenia that could lead to the risk of infection including serious and life-threatening infection
- Diarrhea
- Abdominal cramping, gas and bloating
- Constipation
- Shortness of breath
- Cough or runny nose

- Mouth sores
- Anorexia
- Weight loss
- Alopecia
- Rash
- Fever and chills
- Dizziness
- Pain
- Increased salivation
- Excessive tearing
- Flushing
- Sweating
- Infection

Less Likely Side Effects: those occurring in 5-20% of subjects (or 5 to 20 out of 100 persons) who received Irinotecan

- Allergic reactions (including hives, rash, itching, collapse, low blood pressure)
- Decrease in proteins in the blood stream and/or Malnutrition
- Rash
- Mouth sores
- Hair loss (scalp or body)
- Vomiting
- Weight loss
- Shortness of breath
- Dehydration
- Hypotension
- Neuropathy
- Flushing
- Changes in electrolytes.
- Changes in liver function.
- Taste alterations or loss of appetite
- Difficulty walking

- Dizziness
- Severe Thrombocytopenia bleeding including serious and life-threatening bleeding
- Severe Anemia
- Reversible difficulty speaking

Rare and/or Potentially Serious Side Effects: those occurring in less than 5% of subjects (or in less than 5 out of 100 persons) who received carfilzomib; side effects can be serious enough to be life-threatening or even fatal in rare cases:

- Muscle weakness
- Severe anorexia
- Fever with or without neutropenia
- Liver damage
- Life threatening infection
- Arterial/venous (artery/vein) blood clotting
- Myocardial ischemia
- Colitis, bowel obstruction

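### For Grade 3-4 heart failure, Section 6.3.3 lets carfilzomib restart at Grade 2 and mentions no approval; Section 6.3.5.3 requires resolution or baseline, plus Medical Monitor approval

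*Combined protocol and SAP*

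**What the plan says.** The table in Section 6.3.3 has a row for Grade 3 or 4 CHF, whether or not drug related. Its carfilzomib cell says the subject "must have the dose held until resolution to grade 2 or less, or return to baseline, after which treatment may continue at 1 dose decrement". Withdrawal is the stated alternative, and a subject without resolution after 2 weeks is withdrawn. The cell says nothing about approval. The irinotecan cell leaves that dose unchanged.

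Section 6.3.5.3 covers the same event, again regardless of relationship to drug, and adds other suspected acute cardiac events. It holds the dose until resolution and then states: "After the event has resolved or returned to baseline, treatment may continue at 1 dose decrement, with the approval of the Medical Monitor". Withdrawal is again the alternative. It ends: "If there is no resolution of CHF after 2 weeks, the subject will be withdrawn from the study".

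The criteria for starting a further cycle, in Section 6.2.1 for Phase I and Section 6.2.4 for Phase II, require that non-hematologic "toxicities have resolved as required in section 6.3.3". Neither mentions Section 6.3.5.3.

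**The concern.** Both texts are mandatory about the hold, but they set different conditions for ending it. The CHF row counts Grade 2 as sufficient recovery, and the cycle-start check sends sites to that row. A site that follows the check and the row as written can re-dose a subject whom Section 6.3.5.3 would keep on hold or withdraw.

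What is at stake is re-exposure to carfilzomib during ongoing Grade 2 heart failure, and whether the Medical Monitor agrees to it beforehand. The protocol treats cardiac toxicity as serious. Section 6.3.5.5 reports deaths from cardiac arrest within a day of dosing and says "Cardiac failure events (e.g., cardiac failure congestive, pulmonary edema, and ejection fraction decreased) were reported in 7% of patients". Section 3.2 says "A minimum of 8 investigative study sites will participate on this trial", so subjects in the same clinical state could be managed differently at different sites.

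**Working it through.** The point is a comparison of texts. The plan states no figure to reproduce.

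**Step 1. The two rules side by side.**

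| Element | 6.3.3, CHF row (carfilzomib) | 6.3.5.3 |
|---|---|---|
| Event | Grade 3-4 CHF, any cause | Same, plus other suspected acute cardiac events |
| Hold ends at | Grade 2 or lower, or baseline | Resolution or baseline |
| Dose on restart | One level lower | One level lower |
| Approval | Not mentioned | Medical Monitor |
| Unresolved after 2 weeks | Withdraw | Withdraw |

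The rules agree on the dose on restart, the 2-week limit and the option to withdraw. They differ on the threshold and on approval. The 2-week limit is worded alike but depends on the threshold: under the row, a subject at Grade 2 has already met the condition.

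**Step 2. Who falls between the rules.** Both accept return to baseline. The threshold conflict is therefore confined to subjects who have improved to Grade 2 or lower but have neither resolved nor returned to baseline. The approval difference applies to every restart after Grade 3-4 CHF.

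**Step 3. A worked case.** Take a Phase II subject at 20/36 mg/m2 with no CHF at baseline, who develops Grade 3 CHF and is at Grade 2 on day 14.
- Under the row, restart is allowed at 20/27 mg/m2 (Section 6.3.1). With six carfilzomib doses per cycle (Section 6.2.4), each full later cycle delivers 27 x 6 = 162 mg/m2.
- Under Section 6.3.5.3 read literally, the subject remains on hold and is withdrawn if CHF is unresolved after 2 weeks: 0 mg/m2.

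**Step 4. Is precedence stated anywhere?** Neighbouring sections show how the protocol handles this when it chooses to. Sections 6.3.5.4 and 6.3.5.5 give way to other protocol text, 6.3.5.6 refers back to 6.3.3, and 6.3.5.8 labels its list as exceptions. Section 6.3.5.3 has no such wording. The discretion in 6.3.5.10 covers only modifications not already described, and CHF is described twice.

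**Step 5. Can the frequency be derived?** Applying the 7% from Section 6.3.5.5 to the 88 planned registrations gives 88 x 0.07 = 6.16 cardiac failure events. That 7% includes pulmonary edema and reduced ejection fraction, is not restricted to Grade 3-4, and comes from other studies. Two further shares are needed, and the documents give neither: the proportion at Grade 3-4, and the proportion of those still at Grade 2 and above baseline when restart is decided. Assuming 25% to 75% for the first and 10% to 50% for the second:
- low end: 6.16 x 0.25 x 0.10 = 0.154 subjects
- high end: 6.16 x 0.75 x 0.50 = 2.31 subjects

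The ends differ by a factor of 2.31 / 0.154 = 15, entirely because of the assumed shares. This range is an illustration, not an estimate.

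**The case against.** The best defence is that the texts can be read together. Section 6.3.3 presents its table as a summary of recommended actions, and Section 6.3.5 is headed as additional information. A summary row that is silent on approval does not waive an approval required in the section that supplements it. That is a fair reading of the approval difference, for a site that consults both sections.

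The same argument can be tried on the threshold, by taking resolution in 6.3.5.3 as shorthand for the row's Grade 2 limit. The row does use the word that way, and the cycle-start criteria tie resolution to 6.3.3. But nothing carries that meaning into 6.3.5.3, which names its own end points. The reading narrows the ambiguity without removing it.

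It is also true that obeying the stricter text satisfies both, because the row permits restart and does not require it. A reader might infer that compliance can never be judged; that goes too far. The remaining difficulty is that a site using the row and the cycle-start check has no prompt to look further. The contact offered in 6.3.5.11 helps only a site that already sees a question.

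A reader might infer that nobody outside the site would know of the event before a restart. The documents do not support that. Under Sections 9.4, 9.5 and 9.5.1, an event that meets the seriousness criteria goes to the operations office within 24 hours, even if not thought drug related, and many Grade 3-4 CHF events would qualify. Reporting is not approval to restart, however.

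A reader might also take the row's Grade 2 limit as an error in itself, because the pulmonary hypertension row says "Hold Carfilzomib until < Grade 2. Resume at one dose level lower, if indicated". Thresholds specific to a toxicity are normal, and the neuropathy row also allows Grade 2. The point rests on the conflict with 6.3.5.3 alone.

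**Conclusion.** The conflict is real and narrow. For a subject whose Grade 3-4 CHF has improved to Grade 2 or lower without resolving or returning to baseline, the CHF row permits restart, while Section 6.3.5.3 read literally requires continued hold and then withdrawal. No text ranks the two, and the cycle-start criteria point to the looser one. The approval difference is weaker, since it may be an addition to a silent row, but the row should still state it.

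The consequence for a subject in that position is 162 mg/m2 of carfilzomib per full cycle against none, assuming a first reduction from 20/36 mg/m2. A reader might infer from the 7% figure that several subjects would be affected. The documents do not give the shares needed to say so, and the conclusion does not depend on a count. This is a matter of dosing safety and consistency between sites; the primary analysis is unaffected.

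**What to change.** Reword only the carfilzomib cell of the CHF row in Section 6.3.3, so that it carries the Section 6.3.5.3 rule:

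*Grade 3 or 4 CHF, whether or not drug related: hold until CHF has resolved or returned to baseline. Restart at 1 dose decrement from the current level only with Medical Monitor approval, or withdraw the subject. If not resolved or returned to baseline after 2 weeks, withdraw (see 6.3.5.3).*

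Stating the decrement from the current level covers a subject already reduced to 20/27 mg/m2, whose next level is 20/20. The cycle-start criteria then lead to the right rule without being edited.

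Leave the irinotecan cell and the rules for other acute cardiac events as they are. Extending the row to add irinotecan holds for any acute cardiac event, with restart at the same dose, would go beyond this conflict. For drug-related Grade 3-4 cardiac events it would also be looser than the reductions now in the table's row for other toxicities and in Section 6.3.5.9.

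The cost is one table cell and no new procedures. The downside is that a few subjects may wait longer for carfilzomib or not restart it.
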